**Table 2. Analysis Time Windows for HCV RNA and Resistance Endpoints (Treatment Period)**

Scheduled Visit	Nominal Day (Study Day)	Time Window (Study Day Range)
Day 1/Baseline a	1 a	≤ 1 a
Week 2	14	2 to 21
Week 4	28	22 to 42
Week 8	56	43 to 70
Week 12	84	71 to 98
Week 16 b	112	99 to 126
Week 20 b	140	127 to 154
Week 24 b	168	155 to 182
Final Treatment Visit c		2 to ≤ 2 days after last dose of study drug

a. Day of first dose of study drug.

b. Applicable to subjects with 24 weeks of treatment.

c. The last value within the window will be used to define the Final Treatment visit value.

Note: Data must also have Study Drug End Day ≤ 2 for all windows. The result closest to the scheduled time point will be used.

**Table 3. Analysis Time Windows for HCV RNA and Resistance Endpoints (Post-Treatment Period)**

Scheduled Visita	Nominal Day (Study Drug End Day)	Time Window (Study Drug End Day Range)
Post-Treatment Week 4	28	3 to 56
Post-Treatment Week 12	84	57 to 126
Post-Treatment Week 24	168	127 to 210
Post-Treatment Week 36	252	211 to 294
Post-Treatment Week 48	336	295 to 504
Post-Treatment Week 96	672	505 to 840
Post-Treatment Week 144	1,008	841 to 1,176
SVR 4 b	28	3 to 56
SVR 12 b	84	57 to 126
SVR 24 b	168	127 to 210

a. Post-Treatment Visits are applicable for subjects who received at least one dose of study drug.

b. For SVR windows, the last value in the window will be used.

Note: The result closest to the scheduled time point will be used, except for SVR4, SVR12, and SVR24. Data must also have Study Drug End Day > 2 for all windows. Study Drug End Day 0 is defined as the day of the last dose of study drug.

**Table 4. Analysis Time Windows for Laboratory Data, Vital Sign (Except Height, Waist circumference, and the Calculation of Growth rate), and PRO Instruments**

Scheduled Visita	Nominal Day (Study Day)	Time Window (Study Days Range)
Day 1/Baseline	1 b	≤ 1 b
Week 2	14	2 to 21
Week 4	28	22 to 42
Week 8	56	43 to 70
Week 12	84	71 to 98
Week 16 c	112	99 to 126
Week 20 c	140	127 to 154
Week 24 c	168	155 to 182
Final Treatment Visit d		2 to ≤ 2 days after last dose of study drug
Scheduled Visit	Nominal Day (Study Drug End Day)	Time Window (Study Drug End Days Range)
Post-Treatment Week 4	28	3 to 56
Post-Treatment Week 12	84	57 to 126
Post-Treatment Week 24	168	127 to 210
Post-Treatment Week 36	252	211 to 294
Post-Treatment Week 48	336	295 to 504
Post-Treatment Week 96	672	505 to 840
Post-Treatment Week 144	1,008	841 to 1,176
Final Post-Treatment Visit e		> 2 days after last dose of study drug

- a. Post-Treatment Visits are applicable for subjects who received at least one dose of study drug.
- b. Day of first dose of study drug.
- c. Applicable to subjects with 24 weeks of treatment.
- d. The last value within the window will be used to define the Final Treatment visit value. The upper bound of this Final window is Study Drug End Day ≤ 2.
- e. The last value within the Post-Treatment Period window will be used to define the Final Post-Treatment visit value. The lower bound of this Final window is Study Drug End Day 3.

Note: The result closest to the scheduled time point will be used. For visits through Treatment Week 24, data must also be within 2 days after the last dose of study drug. For post-treatment visits, data must also have Study Drug End Day > 2 where Study Drug End Day 0 is defined as the day of the last dose of study drug.

Lab data are collected only through Post-Treatment Week 4.

Acceptability questionnaire is collected on Treatment Weeks 2, 12, and 24 if applicable for subjects taking the min-tablet formulation only.

**Table 5. Analysis Time Windows for Height, Waist Circumference, the Calculation of Growth Rate, and Tanner Pubertal Stage**

Scheduled Visita	Nominal Day (Study Day)	Time Window (Study Days Range)
Day 1/Baseline	1 b	≤ 1 b
Scheduled Visit	Nominal Day (Study Drug End Day)	Time Window (Study Drug End Days Range)
Post-Treatment Week 12	84	3 to 168
Post-Treatment Week 36	252	169 to 462
Post-Treatment Week 96	672	463 to 840
Post-Treatment Week 144	1,008	841 to 1,176
Final Post-Treatment Visit c		> 2 days after last dose of study drug

- a. Post-Treatment Visits are applicable for subjects who received at least one dose of study drug.
- b. Day of first dose of study drug.
- c. The last value within the Post-Treatment Period window will be used to define the Final Post-Treatment visit value. The lower bound of this Final window is Study Drug End Day 3.

Note: The result closest to the scheduled time point will be used. For post-treatment visits, data must also have Study Drug End Day > 2 where Study Drug End Day 0 is defined as the day of the last dose of study drug.

Tanner pubertal stage is collected for all subjects with age ≥ 9 to 17 year old. If a subject turns 9 year old during the study, the test will start to be performed after the subject turns 9 year old. Once a child reaches Tanner Stage 5, the test will not be repeated.

For the calculation of growth rate only, height will be assigned to a visit as described in the table above, then growth rate will be calculated as the change in height (millimeter) over the change in age (years) from the previous visit. If height is missing at a visit and/or the previous visit, then growth rate will be missing for the visit.

**Table 6. Analysis Time Windows for Acceptability Questionnaire (Treatment Period Only)**

Scheduled Visit	Nominal Day (Study Day)	Time Window (Study Day Range)
Week 2	14	2 to 35
Week 12	84	57 to 126
Week 24 a	84	127 to 182
Final Treatment Visit b	2 to $\leq$ 2 days after last dose of study drug	

- a. For 24-week treatment only.
- b. The last value within the window will be used to define the Final Treatment Visit value. The upper bound of this Final window is Study Drug End Day  $\leq$  2.

Note: Data must also have Study Drug End Day  $\leq$  2 for all windows. The result closest to the scheduled time point will be used. Palatability questionnaire are administrated to subjects in Part 2 at Week 2 and End of Treatment Visit or premature discontinuation visit.

**Table 7. Analysis Time Windows for Fibrotest**

Scheduled Visit a	Nominal Day (Study Day)	Time Window (Study Days Range)
Day 1/Baseline	1 b	$\leq$ 1 b
Scheduled Visit	Nominal Day (Study Drug End Day)	Time Window (Study Drug End Days Range)
Post-Treatment Week 24	168	3 to 420
Post-Treatment Week 96	672	421 to 840
Post-Treatment Week 144	1,008	841 to 1,176
Final Post-Treatment Visit c		> 2 days after last dose of study drug

- a. Post-Treatment Visits are applicable for subjects who received at least one dose of study drug.
- b. Day of first dose of study drug.
- c. The last value within the Post-Treatment Period window will be used to define the Final Post-Treatment visit value. The lower bound of this Final window is Study Drug End Day 3.

Note: The result closest to the scheduled time point will be used. For post-treatment visits, data must also have Study Drug End Day  $>$  2 where Study Drug End Day 0 is defined as the day of the last dose of study drug.

### 6.3 Missing Data Imputation

No data will be imputed for any efficacy or safety analyses except for analyses of the HCV RNA endpoints.

### **Missing Data Imputation for SVR**

HCV RNA values will be selected for analysis based on the analysis windows defined in Section 6.3.

For analyses of SVR, subjects' missing visit values will have backward imputation applied, if possible. For backward imputation, if the nearest HCV RNA value after the SVR window is unquantifiable or undetectable, then it will be used to impute the HCV RNA value in the SVR window. If a subject is missing an HCV RNA value within the appropriate SVR window after performing backward imputation, then this value will be imputed with an HCV RNA value from a local laboratory if present; otherwise, the HCV RNA value will be missing. Subjects with missing HCV RNA data in the analysis window, after imputations, will be imputed as a failure.

Regardless of the imputation method described above, if a subject starts another treatment for HCV, then all HCV RNA values for this subject measured on or after the start date of the new HCV treatment will be excluded from analyses. The subject will be considered a failure for summaries of viral response at all time points after the start of the new HCV treatment.

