If a subject has a missing HCV RNA value at a post-baseline visit but with undetectable or unquantifiable HCV RNA levels at both the preceding value and succeeding value, the HCV RNA level will be considered undetectable or unquantifiable, respectively, at this visit for this subject. For SVR12 and SVR24 analysis, if there is no value in the appropriate window but there is an HCV RNA value after the window, then it will be imputed into the SVR12 or SVR24 window, respectively. Subsequent to this flanking imputation, if a subject is missing a value for the visit window associated with the analysis, the subject will be imputed as a visit failure (i.e., not undetectable or unquantifiable).

The 95% confidence interval for any simple percentage (e.g., SVR12, SVR24, and percentage of subjects with ALT normalization) will be calculated using normal approximation to the binomial distribution if the percentage is not 0% or 100%; otherwise, Wilson's score method will be used.

Detailed statistical methods for all endpoints will be provided in the Statistical Analysis Plan (SAP).

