**Relapse12** = confirmed HCV RNA  $\geq$  LLOQ between end of treatment and 12 weeks after last actual dose of study drug (up to and including the SVR12 window) for a subject with HCV RNA  $<$  LLOQ at Final Treatment Visit who completed treatment excluding reinfection as described below.

**Relapse24** = confirmed HCV RNA  $\geq$  LLOQ within the SVR24 window for a subject who achieved SVR12 and has HCV RNA data available in the SVR24 window, excluding reinfection.

---

**Relapseoverall** = confirmed HCV RNA  $\geq$  LLOQ between end of treatment and up to and including the last HCV RNA measurement collected in the PT Period for a subject with HCV RNA  $<$  LLOQ at Final Treatment Visit who completed treatment excluding reinfection.

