### **Reasons for SVR12 Non-Response**

Subjects who do not achieve SVR12 (SVR12 non-responders) will be categorized as having:

1. On-treatment virologic failure (see **On-treatment virologic failure definition**);
2. HCV reinfection (see definition described earlier);
3. Relapse12;
4. Prematurely discontinued study drug with no on-treatment virologic failure (defined as any SVR12 non-responder who prematurely discontinued study drug [study drug duration < 77 days for subjects assigned to 12 weeks of treatment or duration < 154 days for subjects assigned to 24 weeks of treatment] and did not meet the **On-treatment virologic failure or HCV reinfection definitions**);
5. Missing follow-up data in the SVR12 window (defined as any subject who completed study drug without data in the SVR12 window after applying the imputation rules and not meeting the definitions of [1], [2], [3], or [4]);
6. Other (defined as SVR12 non-responder not meeting the definitions of [1] – [5]).

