**10.7****Additional Efficacy Analyses**

The following efficacy endpoints will be analyzed by formulation, age and weight group, and across all subjects on the adult formulation:

1. The percentage of subjects with virologic failure during treatment;
2. The percentage of subjects with Post-Treatment relapse (including Relapse12 as defined at the end of this section);
3. The percentage of subjects who relapsed after achieving SVR12 (**Relapse24**).
4. The percentage of subjects with HCV RNA < LLOQ at each post baseline visit during the Treatment Period (using data as observed);
5. The change from baseline to all post-baseline visits in Fibrotest score.

All rates of SVR, ALT normalization, virologic failure on treatment and relapse will be presented with 2-sided 95% confidence intervals using the Wilson's method. Imputations for missing data will be performed as described in Section 6.3 for analysis of SVR and relapse. All other endpoints will be presented using data as observed.

A summary of the subjects who completed treatment and relapsed (defined as **Relapseoverall**) will be prepared displaying the number of subjects relapsing overall and by SVR visit window (within the SVR4, SVR12, SVR24 windows or after SVR24 window), including the subject number and the SVR visit window corresponding to the first HCV RNA value of those indicating the occurrence of relapse. A similar listing will be prepared for subjects who prematurely discontinued treatment and relapsed after having HCV RNA < LLOQ at their Final Treatment Visit. A listing of subjects in the ITT

population excluded from the relapse denominator (e.g., study drug duration < 77 days for subjects assigned to 12 weeks of treatment) will be provided, as applicable.

Summary statistics (n, mean, SD, median, minimum and maximum) at each applicable visit and for change from baseline to each applicable visit will be provided by fibrosis stage and SVR12 for Fibrotest score.

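### A treatment completer with no HCV RNA value in the SVR12 window who is viremic in the SVR24 window meets neither Relapse12 nor Relapse24, and both failure-reason tables file the child as non-virologic

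*SAP*

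**What the plan says.** **Imputation.** For an empty SVR window, SAP 6.3 says that "if the nearest HCV RNA value after the SVR window is unquantifiable or undetectable, then it will be used to impute" the value in the window. If the window is still empty, "then this value will be imputed with an HCV RNA value from a local laboratory if present". After that, "Subjects with missing HCV RNA data in the analysis window, after imputations, will be imputed as a failure". SAP 10.7 extends these rules beyond SVR: "Imputations for missing data will be performed as described in Section 6.3 for analysis of SVR and relapse". Protocol 8.1 sets no condition on the later result: "if there is no value in the appropriate window but there is an HCV RNA value after the window, then it will be imputed". This applies to both SVR12 and SVR24.

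**Relapse.** In SAP 10.1, Relapse12 is a confirmed quantifiable value "between end of treatment and 12 weeks after last actual dose of study drug", closing with the SVR12 window, in a completer who was below LLOQ at the Final Treatment Visit. Relapse24 needs a confirmed quantifiable value at 24 weeks, in the "window for a subject who achieved SVR 12 and has HCV RNA data available in the SVR 24 window, excluding reinfection". By contrast, Relapse-overall runs to the last post-treatment measurement and has no SVR12 condition. Virologic failure is on-treatment failure or Relapse-overall.

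**Reasons for failure.** The fifth SVR12 category, missing follow-up data, is "defined as any subject who completed study drug without data in the SVR 12 window after applying the imputation rules", provided no earlier category applies. The last category in each table is Other. Protocol 8.1.2.5 has one relapse category for both SVR12 and SVR24 non-response, subdivided only into relapse and reinfection.

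**The concern.** The two time-limited relapse definitions should together cover every relapse through the SVR24 window. They do so only when the SVR12 status rests on an HCV RNA value. When the SVR12 window is empty and the next result is positive, Relapse12 has closed and Relapse24 never opens. The imputation rule does not close this gap, because it uses a later negative and ignores a later positive.

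A documented virologic relapse is then labelled with a non-virologic reason in the two tables that explain why children failed. The child has a post-treatment value, so the child also stays in the Relapse12 denominator as a non-relapser. With about 62 children and few expected failures, each label in those tables matters to a reader.

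**Working it through.** The plan gives no figure on this point, so the check is a trace through the definitions.

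**Inputs.** The SVR12 window is Study Drug End Days 57 to 126 and the SVR24 window is Days 127 to 210 (SAP Table 3). Completion of 12-week treatment means at least 77 days of study drug (SAP 10.1). A last available post-treatment value at or above LLOQ needs no confirmation (SAP 10.1); this waives confirmation, not timing. The trace assumes a completer below LLOQ at the Final Treatment Visit, with no local laboratory value in the empty window, no new HCV therapy and no reinfection.

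**Results under the SAP** (neg is below LLOQ, pos is at or above LLOQ):

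| PT4 | PT12 | PT24 | SVR12 | Relapse12 | Relapse24 | Relapse-overall |
|---|---|---|---|---|---|---|
| neg | neg | pos | yes | no | yes | yes |
| neg | pos | pos | no | yes | no | yes |
| neg | missing | neg | yes, by carry-back | no | no | no |
| neg | missing | pos | no | **no** | **no** | yes |
| missing | missing | pos | no | **no** | **no** | yes |
| pos | missing | pos | no | yes | no | yes |

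The fourth row is the case at issue:

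1. The Day 127–210 positive is not carried back, so the SVR12 window stays empty and SVR12 is a failure.
2. Relapse12 ends at Day 126 and no quantifiable value occurs by then.
3. Relapse24 requires achieved SVR12, which the child does not have.
4. SVR12 reason: there is no on-treatment failure, reinfection, Relapse12 or early discontinuation, so the fifth category (missing follow-up data) applies.
5. SVR24 reason: data are present in the SVR24 window, so the missing category does not apply and only Other is left.

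The fifth row ends the same way. In the sixth row, the two consecutive positives can be read as Relapse12, so a positive PT Week 4 value removes the problem.

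Under the protocol 8.1 rule, the PT Week 24 positive would be placed in the SVR12 window. The child would then be Relapse12 and still an SVR12 failure.

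**Effect on mITT-GT-VF.** SAP 5.1.1 removes subjects whose SVR12 failure had a reason other than on-treatment virologic failure or relapse. As an illustration, assume 62 treated: 59 with SVR12, one Relapse12, one lost to follow-up and one such child.

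- ITT: 59/62 = 95.2% under either rule.
- mITT-GT-VF with the child dropped: 62 − 1 − 1 = 60, and 59/60 = 98.3%.
- mITT-GT-VF with the child kept: 62 − 1 = 61, and 59/61 = 96.7%.

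**Frequency.** The documents give no missed-visit rate. Adult GT1a non-cirrhotic relapse in protocol Table 1 is 6/314, 1/98 and 5/172, about 1% to 3%. Applied to all 62 children, this gives 62 × 0.01 = 0.6 to 62 × 0.03 = 1.9 relapses. With an assumed 5% to 10% chance of an empty SVR12 window, independent of relapse, the expected number of affected children is 0.6 × 0.05 = 0.03 to 1.9 × 0.10 = 0.19. The GT1a rates probably overstate relapse here: protocol Tables 2 and 3 show no relapse in GT1b without RBV, and protocol section 3.0 reports 100% SVR12 in non-cirrhotic GT4 adults on 2D with RBV. Both groups are eligible for this study.

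**The case against.** The strongest reply is that the event is not lost. It counts in Relapse-overall and in virologic failure. The SAP 10.7 summary of relapses by SVR window lists it by subject number, and the child appears to qualify for the resistance population in SAP 10.10. A reader might infer that the relapse disappears from the report; those outputs show that it does not. A reader might also infer that efficacy is overstated; it is not, because the child fails SVR12 and SVR24 under either rule. Both points stand.

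Three further points stand in part:

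- SAP 10.7 describes Relapse24 as relapse after achieving SVR12. For that population the rate is correct, so Relapse24 is not biased. The gap is that no other time-limited category takes the child.
- The asymmetric carry-back has a rationale. A later negative supports an earlier negative, whereas a Day 127–210 positive does not show viremia by Day 126. This is a reason not to call the event Relapse12, but it does not justify calling it missing or Other. Protocol 8.1 leaves detail to the SAP, but the SAP gives no reason for narrowing the rule.
- SAP 5.1.1 says relapse without naming a definition. Loss of the child from mITT-GT-VF is therefore a possible reading, not an established one.

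One might also infer that a single such child would halve the relapse count. That takes adult GT1a rates for the whole study and supposes a pattern whose frequency the documents do not give.

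**Conclusion.** The gap is real on the text. A completer with no HCV RNA value in the SVR12 window, no earlier viremia after treatment and a positive result in the SVR24 window is a relapse under Relapse-overall. The same child is a non-virologic failure in both reasons tables. This contradicts the SAP's own virologic failure definition and departs from the single relapse category in protocol 8.1.2.5.

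The size is limited. The primary and secondary SVR rates and the 67% comparisons do not move. The labels in two tables and the Relapse12 count are affected. On one reading of SAP 5.1.1, a sensitivity estimate also moves, by 98.3 − 96.7 = 1.6 percentage points per child in the illustration. The conclusion assumes no local laboratory value in the window, no new HCV therapy and no reinfection. The pattern is probably rare. The correction is worth making because it is cheap and can be specified in advance.

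**What to change.** 1. In SAP 10.1, extend Relapse24 or add a line beside it. It should cover treatment completers below LLOQ at the Final Treatment Visit who have no HCV RNA value in the SVR12 window, no earlier confirmed quantifiable value, and a first confirmed (or last available) value at or above LLOQ in the SVR24 window, excluding reinfection. Report them separately from relapse after achieved SVR12, and count each subject once.
2. In the SVR12 and SVR24 reasons tables, classify these subjects as relapse.
3. In SAP 5.1.1, state that relapse for mITT-GT-VF includes them, so that they are kept as failures.
4. Reconcile SAP 6.3 with protocol 8.1 on carrying back quantifiable values. If positives are carried back, limit this to the next scheduled window. Without a limit, a first positive at PT Week 36 or 96 could be dated into Days 57 to 126. State which rule takes precedence, because a carried-back positive would make the child Relapse12 and leave the new line in item 1 empty.

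The cost is a few sentences, one derivation change and a possibly slightly higher reported relapse rate. The rules should be settled before the PT Week 12 interim tables are produced.

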### **Missing Data Imputation for Virologic Failure**

If HCV RNA values from the central laboratory are missing but a local laboratory value is present in the appropriate time period, then the local laboratory value will be used to assess post-treatment relapse and on-treatment virologic failure.

## **7.0 Demographics, Baseline Characteristics, Medical History, and Previous/Concomitant Medications**

The ITT population and 2 ITT population table formats will be used to summarize demographics, baseline characteristics, medical history and previous, concomitant, and post-treatment medications; i.e., data will be summarized by age and weight group and overall among all subjects on the mini-tablet formulation; and by Part 1 vs Part 2 and

---

overall among subjects on the adult formulation, and overall among subjects on mini-tablet formulation and overall among all subjects.

## 7.1 Demographic and Baseline Characteristics

Demographics include age, birth year, weight, height, BMI, height z score (height z score will be calculated using WHO published height-for-age z-score tables), and waist circumference as continuous variables, and sex, race, ethnicity, geographic region and country, age category ([ $\geq$  3 - 8 year old group], [ $\geq$  9 - 11 year old group], and [ $\geq$  12 - 17 year old group]), weight category 15 to 29 kg, 30 to 44 kg,  $\geq$  45 kg), and height z-score category (< -1, -1 to 1, > 1).

Baseline characteristics will include: HCV genotype subtype (1a, 1b, 1-other, and 4; using central laboratory results and final genotype/subtype results, see Section 10.10), IL28B genotype ([CC, CT, or TT] and [CC or non CC]), prior IFN treatment history (treatment-naïve or IFN-based treatment-experienced), response to prior IFN treatment (prior non responder {null responder, partial responder, or other unable to specify}, breakthrough, relapse, unknown and interferon experienced-other), baseline platelet count (continuous and [ $< 90 \times 10^9/L$ ,  $\geq 90 \times 10^9/L$ ], baseline albumin (continuous and [ $< 35$ ,  $\geq 35$  g/L]), baseline creatinine clearance using the Schwartz method for subjects from 3 to < 12 years old (continuous and [ $< 30$ ,  $\geq 30$  to  $< 60$ ,  $\geq 60$  to  $< 90$ ,  $\geq 90$  mL/min/1.73 m^2]) and using the CC&G method for subjects at least 12 years old (continuous; and [ $< 30$  mL/min,  $\geq 30$  –  $< 50$  mL/min,  $\geq 50$  –  $< 90$  mL/min,  $\geq 90$  mL/min]) baseline HCV RNA levels ([continuous (use log10 HCV RNA)] and [ $< 800,000$  IU/mL or  $\geq 800,000$  IU/mL]), baseline fibrosis stage (F0 - 1, F2, F3, F4), baseline Fibrotest score (continuous and [ $< 0.49$ ,  $0.49$  –  $0.58$ ,  $0.59$  –  $0.74$ ,  $\geq 0.75$ ]), baseline Child-Pugh score (non-cirrhotic, 5, 6, or  $> 6$ ), tobacco use (current, former, never or unknown) status, alcohol use (current, former, never or unknown) status, and baseline Tanner pubertal staging – genital (males only) (stages 1 - 5), breast (females only) (stages 1 - 5), and pubic hair development (stages 1 - 5).

Subjects' HCV genotype and subtype may be assessed based on the Inno-LiPA 2.0 Assay used by the Central lab (Covance), the HCV genotype determination by Sanger sequencing a region of NS5B by the Central lab (Covance) and/or from phylogenetic analysis of the full length NS3/4A, NS5A, and/or NS5B sequences performed by AbbVie. If the phylogenetic analysis is available it will be used to determine the subject's final HCV genotype and subtype. If it is not available, then the Sanger assay result will be used to determine the subject's HCV genotype and subtype, if available. Finally, if neither the phylogenetic analysis result nor the Sanger assay results are available, then the Inno-LIPA assay results will be used to categorize the subject.

Subjects' baseline fibrosis stage will be assessed by investigator during the screening period and categorized as F0 - 1, F2, F3, or F4.

Summary statistics (N, mean, median, standard deviation [SD], and range) will be generated for continuous variables (e.g., age and BMI) and the number and percentage of subjects will be presented for categorical variables (e.g., sex and race).

